9.3 POPULATIONS FOR ANALYSES

All intent-to-treat (ITT) analysis population (i.e., all randomized participants) will be included in the data analyses.

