completing the pre-exposure survey. Once the app is installed in participants' own phones and they successfully log in through their Twitter credentials, they will be asked to keep the app on their phone for three months with the notification setting "on". After all these steps are completed, they will be asked to complete the pre-exposure survey. The radon app can be accessed via computer or smartphone: <https://radon-production.herokuapp.com/>

The other half of the participants assigned to the brochure condition will be asked to provide the mailing address prior to completing the pre-exposure survey so that they can receive EPA brochures in the next 3 months via postal mail. Once this step is completed, they will be asked to complete the pre-exposure survey. During the 3-month period, participants assigned to the radon app condition will receive the radon educational materials via the app. Materials include the informational content repurposed from EPA brochures and radon-education Tweets using hashtags, such as #radon, #lungcancer, #healthylungs, and #radonawareness. The app uses the Twitter's mechanism so that's why participants need to use their Twitter credentials to login, and those hashtags used in Tweets are automatically detected by the app, and will be populated in the app. While keeping the app for three months, if participants would like to test their homes for radon levels, as education materials they will be exposed to encourage to do so, they can request a free radon kit through the app. They will be asked to enter their mailing address, email, and phone number so that the kit will be delivered to their home address. Although the app would collect such personal information, this is only to provide them with the free radon kit, and such information won't be attached to their any survey responses. On the other hand, participants assigned to the brochure condition will receive a total of three EPA brochures, with each one being delivered once a month. In each mailing, participants will receive a pre-addressed, pre-paid postcard to request a free radon test kit. The postcard will be addressed to a UND address so that we can track the number requested by participants in the brochure condition.

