Participants who completed the pre-exposure survey then received an email reminder including the link for the post-exposure survey three months after the completion of their pre-exposure survey. Participants who did not complete the post-exposure survey two weeks after the initial email received a reminder email.

A sample size of at least 100 students in each group was determined to have a power of .8 to .9 to detect differences in proportions of at least 20%, Chi-square values of five or more with one or two degrees of freedom, mean differences of at least 0.3, and odds ratios greater than three in logistic regression.

Participant incentives:

Students who were enrolled in COMM 110 class received 0.5 extra course credit point for the completion of pre-exposure survey, which was equivalent to the half-hour research participation. If they completed the second and final session (i.e., post-exposure survey), they received additional 0.5 extra credit point.

Students who were enrolled in COMM 102 class met the half-hour research participation requirement for completing the pre-exposure survey. If they completed the second and final session (i.e., post-exposure survey), they met additional half-hour research participation requirement.

In addition to extra credit or meeting the research requirement, students received a \$10 gift card for the completion of pre-exposure survey. If they complete the second and final session (i.e., post-exposure survey), they received another \$15 gift card.

All students included in the Comm department's SONA research pool are 110 and 102 students, and they are taught by GTAs (110) and a designated instructor (102). The PI has never taught 102 or 110 courses, and will not do so. But in case any of PI's students are invited to the study, they will be given an option to complete an alternative task as a way to avoid coercion or undue influence.

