7.2 PARTICIPANT DISCONTINUATION/WITHDRAWAL FROM THE STUDY

Participants are free to withdraw from participation in the study at any time upon request.

An investigator may discontinue a participant from the study for the following reasons:

- Significant study intervention non-compliance, unless varying compliance is an aspect of the study objectives
- Lost-to-follow up; unable to contact subject (see **Section 7.3, Lost to Follow-Up**)

- Any event or medical condition or situation occurs such that continued collection of follow-up study data would not be in the best interest of the participant or might require an additional treatment that would confound the interpretation of the study
- The participant meets an exclusion criterion (either newly developed or not previously recognized) that precludes further study participation

The reason for participant discontinuation or withdrawal from the study will be recorded by the PI. Subjects who read the informed consent form, and are randomized and receive the study intervention, and subsequently withdraw, or are discontinued from the study, will not be replaced.

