7.3 LOST TO FOLLOW-UP

A participant will be considered lost to follow-up if he or she fails to complete the post-exposure survey and study staff are unable to contact the participant after at least 2 attempts.

The following actions must be taken if a participant fails to complete the post-exposure survey:

- The site will attempt to contact the participant, counsel the participant on the importance of maintaining the assigned visit schedule and ascertain if the participant wishes to and/or should continue in the study.
- Before a participant is deemed lost to follow-up, the investigator or designee will make every effort to regain contact with the participant via a reminder email. These contact attempts will be documented in the participant's medical record or study file.
- Should the participant continue to be unreachable, he or she will be considered to have withdrawn from the study with a primary reason of lost to follow-up.

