9.4.3 ANALYSIS OF THE SECONDARY ENDPOINT(S)

Secondary endpoints:

Effectiveness of the radon app vs. brochure at 3 months re: changes in radon knowledge, as measured by the number of correct responses to a series of 20 true/false questions (e.g., "The EPA recommends that homes with 4 picocuries per liter (pCi/L) or more of radon should be fixed.").

Radon knowledge will be measured by the number of accurate responses to 20 True-False statements in T1 (baseline) and T2 (at 3 months).¹¹ The response options will be: "true," "false," and "I don't know." Participants' responses to each statement will then be re-coded to 1 ("correct") or 0 ("incorrect" or "I don't know"). After that, two radon knowledge index variables (continuous) will be created by summing participants' responses to each statement in T1 (baseline) and T2 (at 3 months). Lower numbers on index variables indicate a low level of knowledge, whereas higher numbers indicate greater knowledge.

H₀: There will be no changes in radon knowledge among those assigned to the radon app condition and those assigned to the brochure condition. **H₁**: There will be more positive changes in radon knowledge among participants assigned to the radon app condition. **Statistical test**: Differences in radon knowledge between the two groups will be tested with directional, independent t-tests, with SAS.

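### The knowledge t-test in 9.4.3 can use only people with a 3-month score and ignores baseline, so loss that relates to baseline knowledge and differs by arm biases it; 9.3 does not say so

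*Combined protocol and SAP*

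**What the plan says.** - **Population (9.3).** The ITT population is everyone randomised, and "all randomized participants) will be included in the data analyses". No endpoint is excepted.
- **Score and test (9.4.3).** Two knowledge indices are built from "responses to each statement in T1 (baseline) and T2 (at 3 months"). The test is: "Differences in radon knowledge between the two groups will be tested with directional, independent t-tests, with SAS". No covariate is named and no change variable is defined, although the alternative hypothesis is about change.
- **Missing surveys (7.2, 7.3, 5.5).** Someone who "fails to complete the post-exposure survey" is chased, and then: "Should the participant continue to be unreachable, he or she will be considered to have withdrawn from the study". Withdrawn participants "will not be replaced". Non-response is foreseen: "Participants who did not complete the post-exposure survey two weeks after the initial email received a reminder email".
- **Burden by arm (5.5).** App participants supply or create a Twitter account and install the app; once "they successfully log in through their Twitter credentials, they will be asked to keep the app on their phone for three months". Brochure participants give a mailing address.
- **What is absent.** No section gives an imputation rule, a weighting scheme, an expected dropout rate or a sensitivity analysis. The recoding rule in 9.4.3 scores wrong and don't-know answers as 0 but does not cover an unreturned survey. Section 9.4.1 offers only transformations or nonparametric tests as corrective steps.

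**The concern.** A t-test needs a T2 score from each person it includes. With no rule for a missing one, software drops that person, so the population in 9.3 is not the one this test compares. That alone would be a labelling problem. It becomes a statistical one because the test also ignores T1. If people who knew more, or less, about radon at the start are the ones who leave, and this happens more in one arm, the remaining groups differ at baseline and the unadjusted comparison carries that difference into the result.

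This is the only planned knowledge test. Knowledge is the secondary objective in 1.1, 3 and 9.2, is listed third under the primary endpoints in 4.1, and is named in section 3 as a possible mediator of the behavioural endpoints. Because the test is one-sided, bias in one direction produces false positives and bias in the other hides a real effect.

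**Working it through.** **Inputs from the plan.** At least 100 per group (9.2); two arms; a directional test.

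**Assumed, because the plan is silent.** Alpha 0.05 one-sided; no true effect; standardised normal scores with T1-T2 correlation ρ = 0.5; app loss 20% with log-odds of leaving 0.8 per SD of T1, in either direction; brochure loss 10% at random. The plan has no figure of its own on this point to reproduce.

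**Step 1: baseline shift among those who stay.** Integrating the logistic loss model over a standard normal T1, the app completers' mean T1 is 0.145 SD below the randomised mean if high scorers leave, and 0.145 SD above it if low scorers leave. With random loss the brochure shift is 0. Call the app-minus-brochure shift m = -0.145 or +0.145.

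**Step 2: bias.**
- Change score: (ρ - 1) × m = -0.5 × (-0.145) = +0.073 SD if high scorers leave; -0.073 SD if low scorers leave.
- T2 alone: ρ × m = 0.5 × (-0.145) = -0.073 SD, or +0.073 SD. The size is the same and the sign is opposite.
- T2 adjusted for T1: 0, because loss that depends only on T1 and arm leaves the T2-given-T1 relation unchanged.

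**Step 3: rejection rate.** The SD of change is √(2(1 - 0.5)) = 1. The SE is √(1/80 + 1/90) = 0.154. Rejection is 1 - Φ(1.645 - bias/SE):
- bias +0.073: 1 - Φ(1.645 - 0.474) = 12%
- bias -0.073: 1 - Φ(1.645 + 0.474) = 1.7%

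Independent simulations of this scenario gave 11.7% to 13.1%, and 1.7% to 1.8%. With baseline adjustment they gave about 5% (4.6% to 5.7%). For correlations from 0.3 to 0.7 the change-score test rejected 9.4% to 14.1%, or 1.5% to 2.0%.

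**Step 4: how far this depends on the loss pattern.**

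| Loss (app 20%, brochure 10%) | Change-score bias (SD) | Rejection |
|---|---|---|
| T1-related in app arm only | ±0.073 | 12% or 1.7% |
| Same slope in both arms | ±0.035 | about 8% or 3% |
| Unrelated to knowledge | 0 | 5% |

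In the second row the brochure arm shifts by 0.075 SD, so m is 0.145 - 0.075 = 0.070 in size and the bias is 0.5 × 0.070 = 0.035.

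**Step 5: precision.** The ratio of ANCOVA residual variance to change-score variance is (1 - ρ²) / (2(1 - ρ)) = 0.75 / 1 = 0.75.

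**Step 6: where adjustment fails.** Let app loss depend on T2 itself (20%, low T2 scorers leave, log-odds 0.8 per SD), with brochure loss again 10% at random. App completers' T2 mean is then 0.145 too high and their T1 mean 0.5 × 0.145 = 0.073 too high.
- Change score: 0.145 - 0.073 = 0.072 SD; simulated rejection about 12%.
- ANCOVA: 0.145 - 0.5 × 0.073 = 0.109 SD; simulated rejection about 20%.

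Here ANCOVA does worse than the test it would replace.

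**The case against.** **The completers-only analysis is not written down.** Correct. It follows from the named test and the absence of any missing-data rule. That the test is on change is also a reading: 9.4.3 could mean T2 alone, in which case the direction of bias reverses. Neither reading escapes the problem.

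**A reader might infer that unequal dropout is enough to bias the test.** It is not. Loss of 20% against 10% unrelated to knowledge gives zero bias. The documents give no rates, no correlation and no mechanism, so they do not show that bias will occur.

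**A reader might infer that a repeated-measures model on everyone with a T1 score would restore the ITT population.** It would not. With two time points and only T2 missing, the likelihood splits into T1 and T2-given-T1, and people with T1 alone contribute nothing to the arm contrast. In one simulated trial with 38 missing T2 scores, the constrained model and the completers' ANCOVA gave the same contrast (0.2499). The protection comes from adjusting for T1, not from a wider population.

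**The plan works to limit loss.** Section 7.1 keeps people who stop the intervention in later assessments, and 5.5 offers a $15 gift card and course credit for the second survey in both arms, plus a reminder. This stands, and it may keep loss small. In addition, 5.5 places the app and Twitter steps before completion of the first survey, whereas 4.1 and 8.1 place them after it. On the order in 5.5, people put off by those steps may lack T1 as well, and baseline adjustment would not cover them.

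**Scope.** Kit orders and returns are recorded as they happen (8.1), not through the survey, so 9.3 can hold for them.

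**Conclusion.** The point holds for the knowledge endpoint. The stated test cannot analyse everyone randomised, and it leaves out the one covariate that would protect it when loss depends on baseline and arm. Under the assumed 20% T1-related app loss and 10% random brochure loss, a one-sided 5% change-score test is biased by about 0.07 SD and rejects about 12% or 1.7%. The distortion is about half that size with a common slope, and absent when loss is unrelated to knowledge. These figures illustrate what the plan leaves open; they do not predict this trial's error rate.

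ANCOVA improves on the stated test but is not a full cure: it is valid only if loss depends on T1 and arm. Under T2-dependent loss its bias can exceed that of the change t-test (about 0.11 against 0.07 SD). The documents do not support reading this as a failure of ITT across the trial, since the behavioural endpoints are unaffected.

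**What to change.** 1. **9.4.3:** replace the t-test with an ANCOVA of T2 on arm and T1, or the equivalent constrained repeated-measures model. State the alpha and sidedness.
2. **9.3:** keep all randomised participants as the denominator for kit orders and returns. For knowledge, say that the arm contrast comes from people with T1 and T2, and that it assumes loss depends only on T1 and arm.
3. **Reporting:** give T2 completion by arm, and T1 scores of completers and non-completers by arm.
4. **Sensitivity analysis:** shift the assumed T2 scores of non-completers by a delta set separately in each arm. The all-randomised difference moves by (app loss × app delta) - (brochure loss × brochure delta). With 20% and 10% loss, -0.5 SD in both arms moves it by -0.10 + 0.05 = -0.05 SD; -0.5 SD in the app arm alone moves it by -0.10 SD. Setting missing T2 equal to T1 is not enough on its own: it fixes every non-completer at zero change and so pulls hardest on the arm that loses more.
5. **Order of steps:** reconcile 5.5 with 4.1 and 8.1 so that it is clear whether a randomised person can lack T1, and say how such people are handled.

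The cost is SAP wording, a few lines of SAS and one extra table. T1 is already collected. At correlation 0.5 the adjusted analysis also has a quarter less residual variance than the change score. The drawback is the one in the verdict, which is why item 4 should accompany item 1.

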9.4 STATISTICAL ANALYSES

9.4.1 GENERAL APPROACH

- For descriptive statistics, categorical and continuous data will be presented (e.g., percentages, means with standard deviations, median, range).
- Inferential tests will indicate the p-value and confidence intervals for statistical significance (Type I error) and whether one or two-tailed.
- Covariates will be pre-specified in the sections below.
- The checks of assumptions underlying statistical procedures will be performed and whether any corrective procedures will be applied (e.g., transformation or nonparametric tests) if needed.

9.4.2 ANALYSIS OF THE PRIMARY ENDPOINT(S)

Primary endpoints:

1. Number of radon test kits requested by participants in the radon app and brochure conditions; and
2. Number of radon test kits used and returned to the laboratory by participants in the two conditions.

Ho: The incidence of: (a) participants' requests for free radon kits and (b) participants utilizing the test kits and returned to Alpha Energy Labs among those assigned to the radon app condition and those assigned to the brochure condition will not differ. **H1:** The incidence of: (a) participants' requests for free radon kits and (b) participants utilizing the test kits and returned to Alpha Energy Labs will be higher among those assigned to the radon app than the brochure condition. **Statistical test:** We will use a directional Z test for difference in proportions to determine whether the incidence of requested and returned kits is higher for those assigned to the radon app condition with SAS. Differences will be described using absolute and relative differences in proportions.

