3 OBJECTIVES AND ENDPOINTS

OBJECTIVES	ENDPOINTS	JUSTIFICATION FOR ENDPOINTS	PUTATIVE MECHANISMS OF ACTION

PRIMARY: The primary objective of this research is to compare the effectiveness of radon information delivered via the radon app vs. a traditional approach (printed brochure) on behavioral outcomes, i.e., the rate at which individuals order free radon test kits and the rate at which they return them to the lab.
	
1. Number of radon test kits requested by participants in the radon app and brochure conditions; and
 
2. Number of radon test kits used and returned to the laboratory by participants in the two conditions.
	
Each measure is the dependent variables to test the primary objective.
	

SECONDARY: The secondary objective of this research is to conduct a clinical trial to compare the effects of the radon app vs. brochures on increasing radon knowledge.
	
Effectiveness of the radon app vs. brochure at 3 months re: changes in radon knowledge, as measured by the number of correct responses to a series of 20 true/false questions (e.g., “The EPA recommends that homes with 4 picocuries per liter (pCi/L) or more of radon should be fixed.”).
	
The radon knowledge variable is a key dependent variable to test the secondary objective. The radon knowledge variable may potentially serve as the mediator of the effects of the interventions on two measures identified as primary endpoints.
	

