8 STUDY ASSESSMENTS AND PROCEDURES

8.1 ENDPOINT AND OTHER NON-SAFETY ASSESSMENTS

Once a participant will be directed to the Qualtrics pre-exposure survey link, the consent form will appear on the first page of the survey. Participants will be asked to read it and proceed if they agree. All participants will be asked to answer pre-exposure survey questions measuring key variables, such as radon knowledge, and demographic information to be used in the analyses (e.g., age, gender, home-owner status, smoking status). They will then be randomly assigned to one of the two conditions (via Qualtrics survey's randomization function). Participants assigned to the radon app condition will receive instructions on how to install the app and be instructed to use the app for the next three months. On the other hand, participants assigned to the brochure condition will receive appropriate instructions and be asked to submit both their mailing and email addresses so that they can receive three brochures in the next three months and be contacted for the post-exposure survey. Next, Participants' email and mailing addresses will not be attached to their responses to the pre-exposure survey to protect participants' privacy and confidentiality. Once participants complete the pre-survey, we have the data telling us that: which email address was assigned to which condition, and the timing. After 3 months, we will send the post-exposure survey link to that email address individually. Participants' behaviors,

which are two primary endpoints (i.e., test kit ordering and utilizing behaviors) will be recorded as they become available during the 3-month period.

In summary, participants in both experimental conditions will complete an online pre-exposure survey during the baseline phase of the study and then are randomized to the app or the brochure group. The experimental groups differ only in the means by which information is conveyed, not in the nature of the information. Participants in both conditions will have the opportunity to order a free radon test kit at any time during the three-month period.

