9.2 SAMPLE SIZE DETERMINATION

Primary endpoints:

1. Number of radon test kits requested by participants in the radon app and brochure conditions; and
2. Number of radon test kits used and returned to the laboratory by participants in the two conditions.

Secondary endpoints:

Effectiveness of the radon app vs. brochure at 3 months re: changes in radon knowledge, as measured by the number of correct responses to a series of 20 true/false questions (e.g., “The EPA recommends that homes with 4 picocuries per liter (pCi/L) or more of radon should be fixed.”).

Sample size determination:

A sample size of at least 100 people in each group will have a power of .8 to .9 to detect differences in proportions of at least 20%, Chi-square values of five or more with one or two degrees of freedom, mean differences of at least 0.3, and odds ratios greater than three in logistic regression.

Statistical analyses:

H₀: The incidence of: (a) participants’ requests for free radon kits and (b) participants utilizing the test kits and returned to Alpha Energy Labs among those assigned to the radon app condition and those assigned to the brochure condition will not differ. **H₁**: The incidence of: (a) participants’ requests for free radon kits and (b) participants utilizing the test kits and returned to Alpha Energy Labs will be higher among those assigned to the radon app than the brochure condition. **Statistical test**: We will use a directional Z test for difference in proportions to determine whether the incidence of requested and returned kits is higher for those assigned to the radon app condition with SAS. Differences will be described using absolute and relative differences in proportions.

H₀: There will be no changes in radon knowledge among those assigned to the radon app condition and those assigned to the brochure condition. **H₁**: There will be more positive changes in radon knowledge among participants assigned to the radon app condition. **Statistical test**: Differences in radon knowledge between the two groups will be tested with directional, independent t-tests, with SAS.

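### The Z test of kit requests is valid but uses no baseline data, although 9.4.1 promises named covariates: a modest efficiency gap, not an error

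*Combined protocol and SAP*

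**What the plan says.** Section 9.4.2 plans this for both primary endpoints: "We will use a directional Z test for difference in proportions to determine whether the incidence of requested and returned kits is higher". The alternative is that incidence "will be higher among those assigned to the radon app than the brochure condition". Results are to be described as absolute and relative differences in proportions. No covariate is named.

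Section 9.4.1 says: "Covariates will be pre-specified in the sections below". Section 8.1 has the pre-exposure survey collect radon knowledge and "demographic information to be used in the analyses (e.g., age, gender, home-owner status, smoking status".

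The only covariate list is in 9.4.7, under sub-group analyses. It has gender, age, race, smoking status, location and time spent on the app. Baseline knowledge and home-owner status are not in it.

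Section 3 says that knowledge "may potentially serve as the mediator of the effects of the interventions on two measures identified as primary endpoints".

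**The concern.** A baseline variable that predicts requests can narrow the interval for the arm difference at no cost in participants. The plan collects candidates, says covariates will be named, and then names none for the main comparison.

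The 9.4.7 models do not fill the gap. They serve the interaction hypotheses, and they condition on app time. App time arises after randomisation and has no counterpart in the brochure arm, and 6.2.1 says its measurement was never developed.

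At stake is some power on the first primary endpoint. There is also a loose end: if covariates are chosen after the data are seen, the choice is open to question.

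**Working it through.** **Inputs.** From 9.2: at least 100 per group, a 20-point difference, power 0.8 to 0.9. From 2.2: 24% of pilot participants ordered a kit through the app and 9% completed a test. Not in the documents, so assumed: the brochure request rate (10% to 14%), the significance level (5%), and the predictive strength of any covariate.

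**Formula.** Power = Φ{[Δ − z·√(2p̄(1−p̄)V/n)] / √([p₁(1−p₁)+p₂(1−p₂)]V/n)}. V is the variance of the adjusted estimate divided by that of the unadjusted one, so V = 1 is the planned test.

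**1. The plan's own figure.** For 30% v 50% with n = 100, the null SE is √(2×0.40×0.60/100) = 0.0693 and the alternative SE is √((0.21+0.25)/100) = 0.0678.
- One-sided: (0.20 − 1.645×0.0693)/0.0678 = 1.27, power 0.898.
- Two-sided: (0.20 − 1.960×0.0693)/0.0678 = 0.95, power 0.828.

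The stated 0.8 to 0.9 reproduces for mid-range rates.

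**2. The planned test nearer the pilot rate.** For 12% v 24%, the SEs are √(2×0.18×0.82/100) = 0.0543 and √((0.1056+0.1824)/100) = 0.0537. One-sided: (0.12 − 1.645×0.0543)/0.0537 = 0.57, power 0.716.

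**3. Gain by share of outcome variance explained (V = 1 − R²), one-sided 5%.**

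| R² | SE lower by | 24% v 10% | 24% v 14% |
|---|---|---|---|
| 0 | 0 | 0.843 | 0.563 |
| 0.01 | 0.5% | 0.847 | 0.567 |
| 0.05 | 2.5% | 0.859 | 0.582 |
| 0.10 | 5.1% | 0.876 | 0.601 |
| 0.20 | 10.6% | 0.907 | 0.646 |

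**4. Simulation of the short covariate list.** Setting: 12% v 24%, 100 per arm, one or two covariates, logistic model, standardised difference.
- No prognostic value: variance up to about 1% higher, power unchanged.
- One covariate at 0.5 to 0.8 log-odds per SD: variance about 2% to 8% lower. Power rises about 2 to 3 points at 0.5 and about 4 to 5 points at 0.8.

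**5. How much of that is precision?** Put V into the formula for 12% v 24%. V = 0.98 gives 0.724, a gain of 0.8 points. V = 0.92 gives 0.747, a gain of 3.1 points. The simulated gains are larger.

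I repeated the simulation with 8,000 runs per scenario and a residual-degrees-of-freedom correction to the SE. Gains were 1.2 to 1.5 points at 0.5 and 3.4 to 4.0 at 0.8. Replacing the pooled SE by the unpooled one in the crude Z test added about 1 point with no covariates at all. So roughly a point of the simulated gain comes from the form of the SE. The range reported below therefore runs from the precision-only figure to the simulated one.

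**6. Why a short list.** At 24% v 10%, five covariates with no effect raised the SD of the estimate from 0.0519 to 0.0528, and (0.0528/0.0519)² = 1.035. The variance loss is thus about 3%. Adjusted test size with five covariates ran from about 5% to about 6%, depending on the setting. At 12% v 24% only 12 + 24 = 36 requests are expected.

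**The case against.** The strongest reply is that nothing here is wrong. The Z test is valid under randomisation and matches the hypothesis, the planned summaries and the sample-size statement. Its standard error already allows for chance imbalance. This stands in full.

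A reader might infer that precision is being thrown away for free, because section 3 expects knowledge to drive kit behaviour. The documents do not support that. The mediator remark concerns knowledge as changed by the intervention and does not say that baseline knowledge predicts requests. Section 2.1 blames limited knowledge in part, but also says that knowledgeable people fail to act. Section 4.1 says most people under 30 do not know what radon is, so baseline scores may vary little among undergraduates. No passage gives an association for any baseline variable.

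Two practical objections also stand.
- **Survey order.** Section 8.1 puts the survey before randomisation. Section 5.5 puts app installation and login, or giving a mailing address, before completing the survey. If 5.5 describes what happens, the baseline knowledge score follows assignment and, in one arm, app access. Adjusting for it could then bias the arm effect.
- **Linkage.** Section 5.5 says details given with an app order are not attached to survey responses, and 8.1 says the same of email and mailing addresses. A Z test needs only counts by arm, whereas an adjusted model needs each order tied to a survey. The study identification number in 10.1.3 suggests a route, and 9.4.7 already depends on one, but the passages are not reconciled.

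**Conclusion.** The point holds as a modest efficiency gap together with an unmet promise to name covariates. The planned test is not biased or invalid.

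At 100 per arm, 12% v 24% and one-sided 5% (all but the arm size and the pilot's 24% assumed), a short adjustment gives:
- about 0 power points if the covariates are not prognostic, with variance up to about 1% higher;
- about 1 to 3 points at 0.5 log-odds per SD;
- about 3 to 5 points at 0.8 log-odds per SD.

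The upper ends are the simulated gains and the lower ends are what the variance reduction alone yields. Which line applies cannot be told from the documents. The benefit also depends on the survey preceding assignment, at least for the knowledge score, and on orders being linkable to baseline responses.

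**What to change.** 1. Reconcile 5.5 with 8.1 on whether the pre-exposure survey precedes assignment. Confirm that orders link to baseline responses through the study identification number.
2. In 9.4.2, make the primary analysis of kit requests a logistic model with arm and one or two pre-randomisation covariates: baseline knowledge score and home-owner status. Use the knowledge score only if it precedes assignment. Otherwise use home-owner status and demographics, which app access would not be expected to change.
3. Report the standardised (marginal) difference in proportions with its confidence interval and a small-sample-corrected standard error. This keeps the planned absolute difference as the target, which an adjusted odds ratio would not.
4. Keep the Z test and crude proportions as the supporting analysis. State how a missing covariate is handled, so that all randomised participants stay in as 9.3 requires.
5. Leave returned kits unadjusted. At about 9 per 100, the pilot's completion rate, events are too few.

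If linkage cannot be confirmed, keep the Z test as primary, say that it is deliberately unadjusted, and amend the sentence in 9.4.1.

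Cost: SAP wording and a few lines of SAS if linkage exists, more if it must be built. The statistical downside is the small variance loss if the covariates prove unrelated to requests.
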